 - Total number of clients who fail to return to the circumcision site (or site indicated by service providers) for recommended follow-up (whether removal visit or AE follow-up).
 - Proportion of all men receiving VMMC services at the evaluation sites who choose ShangRing method instead of surgical circumcision.
- Document provider acceptability of ShangRing, to be measured by the following:
 - Provider perceived ease of application, ease of removal, ease of clinical management of adverse events, and preferences in comparison to conventional circumcision methods.
- Document duration of procedures, and problems encountered during procedures and post-procedure care, to be measured by the following:
 - ShangRing application time will be measured, including the overall time the client is on the procedure table, and the time required for discreet application activities: client preparation time (including application of local anesthetic and sizing), marking and device application, and clean-up time.
 - ShangRing removal time will be measured, including the overall time the client is on the procedure table, the time required for discreet removal activities, and time for post removal instructions given to the client.
- The percentage of clients determined by a clinician to be clinically healed 49-52 days post-placement of the ShangRing device (42 days post-removal), and the time at which point all clients are clinically healed.
 - Healing will be documented by evaluation staff, who will take photographs of the client's genital area during the follow-up visits.
 - Healing will meet the definition of clinical healing after VMMC, defined as:
 - "Intact epithelium (unbroken skin) covering the wound as judged by the provider on visual inspection, meaning that none of the following are present: sutures, scabbing, drainage, moisture, gaps between epithelial edges or ulceration."²⁵

Evaluation Design

Overall Design

This implementation pilot is comprised of two phases: a training phase and the main implementation pilot. During the training phase clinicians at the participating sites will be trained in the use of the ShangRing device. Upon completion of the training phase, the main implementation pilot will begin. The implementation pilot is a single arm, open label, prospective cohort evaluation.

Description of Evaluation Populations and Catchment Areas

Shinyanga, Tanzania

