Measures of ShangRing skills following training in the use of ShangRing application including: theoretical tests, practical test of hands-on-skills and clinical test of performing ShangRing on subjects. Indirect measures will focus on the average procedure time of trainees undergoing ShangRing device training. Additional aspects of the training will be explored through qualitative in-depth interviews (See Appendices XIX-XX). Areas of exploration with qualitative data collection will focus on the strengths and weaknesses of the training, effectiveness of training package/materials, satisfaction with training, and suggestions for improvement of training and facilitation. Provider training and acceptability of the ShangRing device will also be assessed through quantitative measures including a Likert scale designed to measure the ease of the procedure, and how willing providers would be to continue performing ShangRing procedures following the conclusion of the implementation pilot (see Appendix XXI).

Implementation Phase

Following the training phase, a cohort of 575 male clients will be recruited to evaluate the safety of the device, training needs, acceptability and healing time of ShangRing in the context of routine use by clinicians. Detailed CRFs will be maintained for all clients, including those circumcised during the training of mid-level providers. The CRFs and standardized forms will be used to evaluate the three components of the Implementation Phase: safety, acceptability, and healing (Appendices VII-X).

Safety Component

The primary aim of the safety component is to monitor clinical adverse events and device-specific adverse incidents according to type and experience of the provider. Data on both general and device-specific adverse events will be monitored using detailed clinical records maintained for all clients and standardized forms completed at specific data collection points. The records and forms will provide information on procedure and removal times and safety, technical difficulty and complications experienced during the procedure and removal process and pain experienced by the male client.

Acceptability Component

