Phase 2: Implementation Cohort Evaluation	455-495 (Depending upon # performed during training phase)	
Safety Component
 
Primary endpoints:
 
 - Adverse events and device-related incidents 
Secondary endpoints:
 
 - Safety of procedure/removal - Provider perception of technical difficulty and complications during procedure and removal process 
Provider Acceptability Component:
 
 - Provider acceptability - Practicality of device use - Procedure and removal times 
Client Acceptability Component:
 
 - Client satisfaction - Cosmetic results - Comfort: 
 - During procedure to place device - During (nocturnal) erections - During removal 
Healing Component
 
 - Percentage of men clinically healed 49-52 days post placement (42 days post-removal) - Time at which point all men are clinically healed 	
Standardized forms to collect data on adverse events and device-related adverse events
 
Client records
 
Brief surveys to collect data on reasons to decline participation in the evaluation as indirect measure of acceptability
 
Brief surveys to collect data on client experience with the ShangRing as an indirect measure of acceptability
 
Qualitative interview with providers
 
Qualitative interviews with 50 male clients
 
Qualitative interview with providers
 
Brief surveys to collect data on reasons to decline participation in the evaluation as indirect measure of acceptability
 
Client records – including those recording application and removal times
 
Client records indicating healing per VMMC healing definition as completed by providers during day 49 healing assessment visit and subsequent weekly healing visits for those not healed at day 49
 
Photographs of the client's genital area, to be taken post-device removal (day 7), and at the day 49 healing assessment visit and at subsequent weekly healing visits

Evaluation Procedures and Logistics

Evaluation Offices

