Date of ShangRing Device Placement (dd-mm-yyyy): _____

Contact Type (select one):

- **On-site visit (specify name of facility/site):** _____
- **Off-site visit (specify location, i.e. work, home, school):** _____
- **Phone contact (number called):** _____

Type of Visit (select one):

- Removal visit (specify days since device placement): _____
- Day 42 post-placement healing assessment (specify day if client comes in on different day): _____
- Post day 42 follow-up healing assessment (specify days since device placement): _____
- Unscheduled visit (specify days since device placement): _____

Is there a photographer present to take pictures of the procedure (circle one): Yes No

(If 'No,' do not proceed until a photographer is available. Photos must be taken with the photo frame, including client ID number, date and pain score before and after device removal).

Has there been a change to the client's medication since device placement (circle one): Yes No

(If 'Yes,' please record the medication on the medications CRF page).

Summary of Follow-Up:

Clinical course leading to client's visit today: _____

Care/advice provided:

Medication given (circle one)? Yes No

If yes, drug (name, dose and total quantity dispensed):

For removal visit, was anesthesia required during removal (circle one): Yes No NA (not removal visit)

If "Yes," what? _____

For removal visit, were there any device-related events or AEs that occurred during the removal (circle one):

Yes No NA (Device not removed this visit)

If "Yes," please record on Adverse Events form.

For removal visit, provider evaluation from 1 to 10 (1 being worst): _____

Name of provider who removed the ShangRing device: _____

Healing status observed by clinician (select one): Healed Not Healed NA (pre-day 42 visit)

Clinical healing defined as: clinical healing after MC by any method is intact epithelium (unbroken skin) covering the wound as judged by the provider on visual inspection, meaning that none of the following are present: sutures, scabbing, drainage, moisture, gaps between epithelial edges or ulceration.

Was client instructed not to masturbate until completely healed (select one)? Yes No NA (client healed)

Was client reminded to abstain from sexual intercourse until completely healed (select one)?

Yes No NA (client healed)

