Appendix XXVI – ShangRing Evaluation Provider Survey

ShangRing Evaluation Provider Survey

Introduction

You are receiving this survey because you participated in the {insert project name} as a provider. This survey is meant to gauge your opinions on the ShangRing circumcision device. Your opinions will be used to inform the acceptability of the ShangRing device among providers, and will guide further implementation of the ShangRing device in Tanzania's voluntary medical male circumcision program.

All opinions expressed in this survey are anonymous and confidential. Your words may be used in future reports and analyses created as part of this program, but they will not be attributed to you.

Please answer all questions below per the directions provided. Many questions are rated on a 1 – 5 scale. Some questions are open ended and offer you the chance to expand upon your answers.

When complete, please return this survey to:

Section 1 – ShangRing Training

This section is meant to evaluate the training you received on the ShangRing device prior to the beginning of the program. Please select the rating for each question based upon the following criteria:

5=Strongly Agree 4=Agree 3=Neither Agree nor Disagree 2=Disagree 1=Strongly Disagree

1. The trainers possessed strong subject matter expertise:

5 4 3 2 1

2. The trainers had the ability to explain and illustrate concepts:

5 4 3 2 1

3. The trainers successfully and completely answered participant questions that arose:

5 4 3 2 1

4. The information received during training was useful and applicable:

5 4 3 2 1

5. The pace of the training was appropriate:

5 4 3 2 1

6. The training was appropriate for your level of experience:

5 4 3 2 1

7. The training materials were useful and applicable:

5 4 3 2 1

8. The training adequately prepared you for performing male circumcision with the ShangRing device:

5 4 3 2 1

9. What did you like most about the training? _____

10. What recommendations do you have for improving the training? _____

Section 2 – Performing ShangRing Circumcisions

This section is meant to evaluate your feelings on using the ShangRing device to perform voluntary medical male circumcisions. Please select the rating for each question based upon the following criteria:

5=Strongly Agree 4=Agree 3=Neither Agree nor Disagree 2=Disagree 1=Strongly Disagree

11. I found ShangRing circumcisions to be easy to perform:

5 4 3 2 1

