12. Compared to surgical circumcision, ShangRing circumcisions were easier to perform:

5 4 3 2 1

13. Compared to surgical circumcision, ShangRing circumcisions were faster to perform:

5 4 3 2 1

14. Compared to surgical circumcision, I find ShangRing to be a safer procedure:

5 4 3 2 1

15. I prefer performing ShangRing procedures over surgical circumcision:

5 4 3 2 1

16. Clients receiving ShangRing appear happier with their circumcision than clients receiving surgical circumcision:

5 4 3 2 1

17. I would advise that clients select ShangRing circumcision over surgical circumcision (if they are eligible for ShangRing):

5 4 3 2 1

18. If possible, I would like to continue offering ShangRing circumcision to clients:

5 4 3 2 1

19. Is there anything in particular you would like to comment on in comparing conventional surgical circumcision with ShangRing circumcision? _____

20. Do you have any final comments on ShangRing or male circumcision in general? _____

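### No instrument shown asks how easy adverse events are to manage, and ease of application is not separated from ease of removal, though all three define provider acceptability

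*Protocol*

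**What the plan says.** Under Secondary Endpoints, the Protocol measures provider acceptability by "Provider perceived ease of application, ease of removal, ease of clinical management of adverse events, and preferences in comparison to conventional circumcision methods". Table 2 adds, among the secondary safety endpoints of Phase 2, "Provider perception of technical difficulty and complications during procedure and removal process".

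The Training Phase section announces quantitative measures of provider acceptability, "including a Likert scale designed to measure the ease of the procedure". The Analysis Overview names the qualitative provider interviews as the source for summarising provider acceptability.

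The instruments are printed as appendices:

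- **Provider survey (Appendix XXVI).** Item 11 is "I found ShangRing circumcisions to be easy to perform" and item 12 is "Compared to surgical circumcision, ShangRing circumcisions were easier to perform". Item 14 is "Compared to surgical circumcision, I find ShangRing to be a safer procedure" and item 15 is "I prefer performing ShangRing procedures over surgical circumcision".
- **Client follow-up form (Appendix XII).** It carries the field "For removal visit, provider evaluation from 1 to 10 (1 being worst", with no statement of what is evaluated.
- **Interview guides (Appendices XXIV and XXV).** The questions are open. The nearest is Phase 2 question 10, on what the provider personally finds difficult.

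**The concern.** The endpoint names three kinds of ease, and the proficiency checklist under Physician Training likewise lists placement, removal and the handling of adverse events as separate skills. A provider may find placement easy but removal or complication care hard. Items 11 and 12 ask that provider for an overall opinion only.

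At stake is a descriptive result meant to inform ministry policy and provider training. If the three kinds of ease are not asked about, a favourable overall rating cannot show which step it reflects. Silence in an interview could mean that a step was easy or simply that it did not come up. A statistical analysis plan cannot repair this, because the answers would not have been collected.

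**Working it through.** The Protocol gives no figure to reproduce. The check maps each part of the endpoint to every provider-completed instrument shown.

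| Part of the endpoint | Provider survey (App. XXVI) | Interview guides (App. XXIV, XXV) | Client-level forms | Coverage |
|---|---|---|---|---|
| Ease of application | Items 11 and 12, whole procedure only | Open questions only | Placement form (App. IX): times, check against the instructions for use, adverse event severity, free comments; no provider rating | Partial |
| Ease of removal | Items 11 and 12, whole procedure only | No question or probe on removal | 1-10 score in App. XII, content undefined; tick-box for removal difficulty in App. XVIII, which records an occurrence and not a perception | Partial or indirect |
| Ease of managing adverse events | None; item 14 asks about safety | No question or probe | App. XVIII records action and outcome, not ease | Not elicited |
| Preference over conventional methods | Items 12 to 17 and open item 19 | Phase 2 question 12 | Not needed | Covered |

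The count is one part covered, two partly or indirectly covered, and one not elicited.

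Two details bear on the middle rows. First, a provider completing the 1-10 field could be scoring ease, the state of the wound or the cosmetic result; nothing on the form decides between them. Second, placement has no matching score, so even a well-labelled removal score would have no counterpart.

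The scale of the affected data follows from the Protocol's own numbers:

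- **Providers.** The Training Phase section gives 8 to 12 trained providers plus another 2 to 4 at each of two sites: 8 + 2×2 = 12 up to 12 + 2×4 = 20.
- **Adverse events at the planning rate.** 2% of 575 is 0.02 × 575 = 11.5 clients. Spread evenly, that is 11.5/20 ≈ 0.6 to 11.5/12 ≈ 1.0 per provider.
- **Adverse events at a higher cited rate.** The 7.6% reported for the device arm of the comparative Kenyan evaluation (Potential Harm section) would give 0.076 × 575 = 43.7 clients, or 43.7/20 ≈ 2.2 to 43.7/12 ≈ 3.6 per provider.

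The even spread is an assumption. At the planning rate, some providers may manage no adverse event at all, so an item on this needs an option for having managed none.

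**The case against.** The strongest reply is that the endpoint speaks of perception, names no scale and does not require a score for each part. The Analysis Overview relies on interviews, and the survey is an additional measure. The Phase 2 guide asks what providers like and dislike, what has changed since their first procedure, what they find difficult and how the device compares with surgery. A provider troubled by removal or by complications has several openings to say so. With 12 to 20 respondents and few adverse events each, open interviewing is a reasonable method.

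Much of this stands. A reader might infer that the endpoint cannot be reported at all, that the survey yields one blended ease score, or that the difficult step would be hidden. The documents do not support those readings:

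- Preference is fully covered, and there are two overall ease items, not one.
- Removal has its own provider-completed field, although an undefined one.
- Removal time is measured separately from application time, and events at removal are recorded.
- Adverse event rates are reported by cadre, and the question whether each cadre can be trained as safe providers is assigned to those rates.

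Nor can it be said that ease is recorded nowhere else. The table bodies of the Application and Removal Time Forms (Appendices XX and XXI) are not shown, so a difficulty field there cannot be ruled out.

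What the reply does not remove is the absence of any prompt. The guides never raise removal or adverse event management, so coverage depends on spontaneous remarks and would differ from provider to provider.

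**Conclusion.** The concern holds in a limited form. The endpoint and the printed instruments do not match on three of four parts: ease of adverse event management is not elicited by any instrument shown, and ease of application and of removal cannot be reported separately or consistently across providers.

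The size is small. One descriptive secondary endpoint is affected, with no hypothesis test attached. The primary endpoint, the sample size and the safety data are untouched.

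The conclusion rests on two assumptions: that the appendices shown are the instruments to be used, and that the unseen tables of Appendices XX and XXI contain no provider rating of difficulty.

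**What to change.** - **Appendix XXVI.** Replace item 11 with three items on the same 1-5 scale: the device was easy to apply; it was easy to remove; adverse events with it were easy to manage. Give the third an option for providers who managed none.
- **Appendix XII.** Label the 1-10 removal-visit score as ease of removal.
- **Appendix XXV.** Add probes on removal and on adverse event management to question 10.
- **Optional.** Add a matching 1-10 rating of ease of application to Part 2 of Appendix IX. Both steps could then be shown per client and by cadre. The endpoint as worded does not require this.

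The required changes cost two extra survey items per provider (three replacing one) and slightly longer Phase 2 interviews. The optional rating adds one field to the placement form. No visits or staff are added.

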Evaluation Goal:

To evaluate the safety and acceptability of the ShangRing device for nonsurgical circumcision in routine clinical settings, as a part of a comprehensive HIV prevention program for males in VMMC programs.

Evaluation Endpoints:

Primary Endpoint: the proportion of males experiencing mild, moderate and severe adverse events (AEs) associated with ShangRing circumcision procedures, including both intra- and post-operative events, and all device-related malfunctions (e.g., early spontaneous detachment).

Secondary Endpoints:

- Training needed for proficiency using the ShangRing device, including number of procedures to become fully proficient at applying and removing the ShangRing device.
- Client and provider acceptability, client satisfaction, and duration of procedure.
- The percentage of clients clinically healed 49-52 days post-placement of the ShangRing device, and the time at which point all clients are clinically healed.

Evaluation Design

Training Phase: this phase will be used to evaluate the training requirements for implementation by mid-level providers, to preliminarily assess acceptability to providers, and to monitor logistical needs. Each clinician will perform no fewer than 10 ShangRing device placements, and 5 ShangRing removals before start of the next phase (implementation pilot).

Implementation Pilot: following the training period, 575 male clients will be recruited to undergo circumcision with the ShangRing device in the context of routine service delivery.

Data will be collected at up to at least 5 points in time: at enrollment and device placement (day 0), at device removal (day 7), during a follow-up phone call (day 10), in-depth qualitative interviews for 50 purposefully selected clients (day 28), at an in-person follow-up visit to assess wound healing (day 49), and at subsequent weekly visits to assess healing for those not completely healed at day 49.

Upon completion of the implementation pilot, the data will be analyzed and used to assist with policy decisions and recommendations on ShangRing use in adult male circumcision programs.

Section C: Protocol

Introduction

Voluntary Male Medical Circumcision (VMMC), VMMC Devices and ShangRing

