Males who present with exclusion criteria for one of the medical reasons listed above will be referred to the appropriate specialist for management of their conditions. Additionally, any men who have an anatomic contraindication but still want circumcision, can be referred to an urologist for further management. In keeping with standard national practice, clients presenting with specific disease conditions such as STIs or TB may be treated on-site or referred for care elsewhere if appropriate services are not available on site. Furthermore, males who are HIV+ will be assessed to determine if they are on antiretroviral therapy (ART). Those not on ART will be referred for ART.

Client Withdrawal Criteria

A client has the right to withdraw from the evaluation at any time, for any reason, without prejudice to his future medical care by the provider or the health facility (see Appendices V and VI for the client and minor client assent forms). If a client withdraws after consent, but prior to device placement, the client will be replaced until the desired sample size is reached and the data will be excluded from analysis. If a client withdraws after device placement, the client will not be replaced and the existing data will be included in the analysis, but no attempts will be made to collect further data other than that required for clinical documentation of the removal visit. The reason, timing and circumstances of the withdrawal will be documented and analyzed. The client will subsequently not be included among those selected for the day 28 in-person interview, nor will they be asked to return for the day 49 follow-up visit to assess healing. When the client withdraws, they will be informed that they may still return to the clinic for removal of the device as scheduled, and contact the clinic should they have further questions, suffer an AE, or experience other difficulties healing.

A client will be informed in advance that if he wishes to withdraw from the evaluation after ShangRing placement but before scheduled removal, he must still return to the provider for device removal on day 7 for his own health. The client will also be advised that once applied, it is not safe to remove the device before day 5. If the client requests removal on day 5 or 6, it will be removed as requested. The number and reasons for client withdrawals will be recorded and included in the final evaluation report (See Appendix XXII).

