Clients' evaluation files at the site, including informed consent and CRF, will be kept in a locked file cabinet with access limited to evaluation staff. Clients' information will be filed by client ID number, with names written in a discrete location (e.g., on the inside cover of the client's file folder) in order to reduce the chance of an inadvertent breach of confidentiality. Clients will not be reported by name in any report or publication resulting from data collected in this evaluation.

All computerized database records will identify clients by identification numbers only. Electronic data files will be maintained on password-protected computers accessible only by site coordinators and investigators.

Potential Risks

While medical male circumcision is generally a safe procedure, clients are at risk for a number of adverse events including pain, injury to the penis, risk of excessive bleeding, and infection, among others. Some of these adverse events have resulted in death in the past. As noted above, the rate of adverse events in circumcision programs, and through previous ShangRing trials, is very low. All men will be counseled on the risk of adverse events when enrolling in the evaluation, and will have the option to withdraw from the procedure until the device is placed.

HIV Notification Policy

All men enrolling in this evaluation must consent and agree to receive an HIV test. Men not wishing to receive an HIV test will be offered conventional surgical circumcision. Men who do receive an HIV test, and test positive, will be notified of their status per Tanzanian Voluntary Medical Male Circumcision Program guidelines. Additionally, men who test positive will be actively linked to HIV care and treatment, also per program guidelines.

Sponsor Monitoring

As the evaluation sponsor, the Centers for Disease Control and Prevention (CDC) may conduct monitoring or auditing of evaluation activities to ensure the scientific integrity of the evaluation and to ensure the rights and protection of evaluation clients. Monitoring and auditing activities may be conducted by:

- CDC staff (“internal”)
- authorized representatives of CDC (e.g. a contracted party considered to be “external”)
- both internal and external parties

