
Please add any additional comments related to this AE. Please write in block letters and sign and date your comments.

I have checked all data introduced to this form until this point and verified that they are complete, correct and reconcilable with the original documentation.

Evaluation Coordinator's Signature: _____ Date: _____

Appendix XIX: Adverse Event Classifications and Definitions: During Device Placement or Wearing and During or After Device Removal*

Adverse Event	Mild	Moderate	Severe
During Device Placement or Wearing			
AN: Anesthetic Related Problem (A1-AN)	Mild localized swelling allergic reaction at injection site without swelling and systemic reaction.	Reaction to anesthetic including light-headedness, nervousness, dizziness that resolves spontaneously and not requiring use of medicines or equipment from the emergency cart/kit/list of emergency commodities at VMMC site and no transfer to another facility or admission to hospital.	Symptoms of severe systemic allergic reaction to local anesthetic including rash, urticaria, angioedema, and shortness of breath, or symptoms of overdose of local anesthetic including light-headedness, nervousness, confusion, dizziness, drowsiness, ringing of ears, blurred or double vision, sensations of heat, cold or numbness, twitching, tremors, convulsions, unconsciousness, respiratory depression, bradycardia, or hypotension requiring use of medicines or equipment from the emergency cart/kit/list of emergency commodities or hospitalization to manage.
BL: Bleeding	A1/A2-BL: Bleeding during placement or wearing that is more significant than usual or spotting of the bandage or clothing with blood; both easily controlled	A1/A2-BL: Bleeding during placement or wearing that requires a pressure dressing to control without surgical re-exploration of the wound or removal of the device.	A1/A2-BL: Bleeding during placement or wearing that requires blood transfusion, transfer to another facility, or hospitalization; or bleeding that requires surgical exploration, removal of device, placement of sutures, hospitalization, or transfer to another facility.
PA: Pain	A1-PA: Client expresses discomfort, however is able to remain still and cooperate for the procedure.	A1-PA: Client expresses discomfort and is not able to cooperate well with procedure.	A1-PA: Client rates pain as very severe.

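### A client who reacts to the anaesthetic and withdraws before the ring is placed drops out of the primary adverse-event rate, although the endpoint counts that reaction

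*Protocol*

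**What the plan says.** Client Withdrawal Criteria sets two rules, divided by device placement. The first, for a client who has consented and then leaves, is that "prior to device placement, the client will be replaced until the desired sample size is reached and the data will be excluded from analysis". The second applies once the ring is on: "If a client withdraws after device placement, the client will not be replaced and the existing data will be included in the analysis". The first rule says nothing about a client who has already had an AE. The same section states that the number of withdrawals and the reasons for them go into the final report.

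Other parts of the protocol bear on this rule:

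- **Evaluation Endpoints (Executive Summary).** The primary endpoint is the proportion of males with AEs of the ShangRing procedure, "including both intra- and post-operative events". The Primary Endpoint section in the main text likewise covers procedure and post-procedure events.
- **Secondary Endpoints, duration of procedures.** The timed steps are listed as "client preparation time (including application of local anesthetic and sizing), marking and device application", so anaesthesia belongs to preparation and comes before the ring.
- **Appendix XIX.** Anaesthetic-related problems are a coded AE (A1-AN) with mild, moderate and severe grades. The severe grade includes "Symptoms of severe systemic allergic reaction to local anesthetic including rash, urticaria, angioedema, and shortness of breath".
- **Potential Risks.** Men "will have the option to withdraw from the procedure until the device is placed".
- **Adverse Event (AE) and Other Device-Related Incident Documentation.** Mild, moderate and severe AEs are compiled to determine the AE rate, with no condition that a device was placed.
- **Analysis Overview.** The AE rate is the percentage of clients with one or more AEs, with a two-sided 95% confidence interval.

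**The concern.** A safety rate should count everyone exposed to the procedure. Here exposure begins with the anaesthetic, but the analysis begins with the placed ring. Between those two moments a client can have an event that the primary endpoint counts, and that event can be his reason for leaving. The withdrawal rule then takes both man and event out of the analysis and brings in another man.

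Exclusion triggered by the outcome moves the rate in one direction only. The result describes men who got as far as a placed ring, not men who began the procedure. The evaluation is meant to inform national policy on the device, so its safety rate should describe the men on whom the procedure was begun.

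This is not a detail left to a statistical analysis plan. The protocol itself fixes the exclusion, and an analysis plan that counted these men would contradict it.

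**Working it through.** **1. The plan's own figure.** Sample Size, Data Collection and Analysis Timeline assumes an AE rate of 2%, 95% confidence and a half-width of 1.5 points.

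n = z² p(1 − p) / d² = 1.959964² × 0.02 × 0.98 / 0.015² = 334.63, rounded up to 335. Adding the stated 240 gives 575. The sample size reproduces and is not in dispute.

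**2. Whether the gap exists.**

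| Step | Place in the protocol | Consequence |
|---|---|---|
| Consent signed | Client Withdrawal Criteria | Start of the replace-and-exclude window |
| Local anaesthetic and sizing | Secondary Endpoints | Exposure begins; an A1-AN event can occur (Appendix XIX) |
| Client may still leave | Potential Risks | The window is still open |
| Device placed | Client Withdrawal Criteria | The window closes; data are kept from here on |

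A graded AE can thus arise inside the window. Client Withdrawal Criteria then excludes it, while the AE documentation section would count it. The two cannot both be followed for the same man.

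**3. Size per case.** At 2%, 0.02 × 575 = 11.5 men with an AE are expected; take 12 as a whole number. Let k be the number of men who have an anaesthetic AE and withdraw before placement. The documents do not give k, so the values below are assumptions. All 575 men are taken as analysed. The rule reports 12/575, replacements included. Restoring the k men gives (12 + k)/(575 + k):

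| k | Rate | Exact (Clopper-Pearson) 95% upper limit |
|---|---|---|
| 0 (as reported) | 12/575 = 2.09% | 3.62% |
| 1 | 13/576 = 2.26% | 3.83% |
| 2 | 14/577 = 2.43% | 4.04% |
| 3 | 15/578 = 2.60% | 4.24% |

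For one man with an AE, with a events among n men, the change is (a + 1)/(n + 1) − a/n = (n − a) / [n(n + 1)] = 563 / (575 × 576) = 0.0017. That is 0.17 points, and it is positive whenever a < n. Exclusion therefore always lowers the rate. The upper limit moves by about 0.21 points per case.

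**4. Men who stop after the anaesthetic without an AE.** Keeping one such man in the denominator gives 12/576 = 2.083% against 12/575 = 2.087%, a fall of less than 0.004 points. Counting them too costs almost nothing and keeps the definition even-handed.

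**The case against.** **The protocol may treat anaesthesia as part of placement.** Appendix XIX files anaesthetic problems under the heading for device placement or wearing. Part 2 of the device CRF (Appendix IX), the placement procedure, contains the anaesthesia item and then asks about AEs during placement. On that usage an anaesthetised man is no longer before placement. This stands as a real ambiguity. It does not remove the problem: the withdrawal rule contrasts before with after placement, and the man in the second group has a ring that must come off. Potential Risks also speaks of the moment the device is placed. A completed placement is the more natural cut-off, and under either reading two sites could classify the same man differently.

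**The event is not hidden.** This is correct. The data are excluded from analysis, not destroyed. Withdrawals and their reasons are reported, AEs are documented, and severe AEs go to CDC within 24 hours. What is lost is the event's place in the primary rate.

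**Severe cases.** A reader might infer that the rule decides whether the report shows any severe AE at all. The text does not support that. A severe reaction would normally lead the provider to stop, whereas the rule covers a client who withdraws. The protocol does not say how a procedure stopped by the provider before placement is counted.

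**Size.** A reader might also try to derive a bias from the anaesthetic complication mentioned for the Kenyan comparison with surgery (Potential Harm and Measures to Mitigate Harm). That does not work either. All 197 ShangRing men there were circumcised successfully, so it shows no missed placement. Its arm is not stated. The ShangRing AE rate in that study was 7.6%, so a frequency taken from it should not be set against the planned 2%.

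**A device-placed denominator matches the target of 575 ShangRing circumcisions.** That is reasonable for counting procedures and for healing and removal, but not for a rate defined to include intra-operative events.

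**Conclusion.** The point holds and is minor. As written, the withdrawal rule can remove a client from the primary AE rate because of an AE that the endpoint counts, and it conflicts with the section that compiles all AEs for the rate. The effect is about 0.17 points on the rate and 0.21 points on the exact upper limit per case, always towards fewer AEs. These figures assume about 12 men with an AE among 575 analysed.

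The number of cases is unknown. The protocol gives no frequency, and such cases are probably rare, so no overall bias can be stated. The conclusion rests on reading device placement as the completed placement. If the authors meant it to begin with the anaesthetic, the defect becomes one of wording, and the sections still need to be reconciled.

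**What to change.** In Client Withdrawal Criteria, for the primary AE rate only, move the cut-off from device placement to the start of the procedure, defined as the first anaesthetic given. Suggested content:

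- *A client who withdraws after consent but before any anaesthetic is given is replaced, and his data are excluded from analysis.*
- *A client whose procedure stops after the first anaesthetic but before placement, by his own choice or the provider's, may be replaced towards the 575 placements. He stays in the denominator of the primary AE rate and, if he had an AE, in the numerator.*
- *Healing and removal endpoints use clients with a device placed.*

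Then align the use of placement in Potential Risks, the AE documentation section, Part 2 of Appendix IX and Appendix XIX with this definition. The change concerns the analysis set only and alters no clinical step.

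The cost is a sentence or two, an AE denominator slightly different from the number of placements, and possibly a slightly less favourable rate. No visit or form is added, because the placement CRF already records the anaesthesia used and any AE during placement.
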